#### **4.2.7.3 Electrocardiograms**

The 12-lead ECG is performed at Visit 2 only. Listings of ECG interpretations will be generated on request.

#### **4.2.7.4 Vital Signs**

Unless otherwise specified, vital signs and other physical data obtained after the start of study medication dosing up to 4 days (inclusive) after the last double-blind dosing date will be considered as obtained during the double-blind treatment period. Vital signs and other physical data obtained from the day after the last study medication +4 days (exclusive) up to the last visit date of the follow-up period will be considered as obtained during the follow-up period.

Visit windows are provided in Section 4.3.1 in order to link each vital sign measurement to a scheduled visit.

The values and changes from baseline for systolic and diastolic blood pressures and heart rate will be summarized by treatment group at each scheduled visit using descriptive statistics (using available data regardless of rescue for patients in Safety Data Set).

Number and percentages of patients with orthostatic hypotension (fall in systolic blood pressure of >20 mmHg or diastolic blood pressure of >10 mmHg (supine to standing)) will be summarized by treatment group at each scheduled visit using available data regardless of rescue in Safety Data Set. All observations regardless of distance to the target in each scheduled visit window will be used for the summary of orthostatic hypotension.

Changes from baseline in weight, BMI, CCI will be summarized presenting n's, means, medians, minimums, maximums, and SEs, at each scheduled visit during the double-blind treatment period and the follow-up period.

#### **4.2.7.5 Pregnancy Test Results**

A by-patient listing of pregnancy test results will be provided using Safety Data Set.

### **4.3 Conventions**

#### **4.3.1 Visit and Period Windows**

Patients do not always adhere strictly to the visit timing in the protocol. Therefore the designation of visits during the double-blind treatment period and follow-up period will be based on the day of evaluation relative to the reference start date rather than the nominal visit recorded in the CRF.

To assign a measurement to a Week t during a study period, the first step consists of selecting all measurements falling within this study period as defined below. To further determine the Week t measurement, mutually exclusive relative day windows are used.

The day windows are defined to provide derived visits that correspond to the post-baseline time points specified in the protocol. As already stated, some restrictions may exist on some laboratory assessments to be included in efficacy analyses. These restrictions will be reflected in the day ranges. For example, since no HbA1c is to be collected at Week 1, the windows for HbA1c will only start at Week 4. No Week 1 windowing will be defined.

For each visit, a window will be defined such that the lower and upper bounds of each window is generally the midpoint between 2 consecutive study visits. The visit windows and applicable study day ranges are presented below in [Table 17](#).

**Table 17 Visit Windows**

Visit	Target Day	Adjusted windows for analyses		
		A1C FPG Safety Laboratory	Vital Signs Weight BMI CCI	CCI
Baseline	1	≤1	≤1	≤1
Week 1	8		2-18*	
Week 4	29	2-57*	19-57*	
Week 12	85	58-127*	58-127*	
Week 24	169	128-Last day of DB period	128- Last day of DB period	2- Last day of DB period
Follow-up Week 27	190	Day 1 of FU period-- Last day of FU period	Day 1 of FU period-- Last day of FU period	Day 1 of FU period-- Last day of FU period

\*: before the last day of DB period.

For some efficacy parameters, the use of double-blind treatment observations is specified in Section 4.3.2. This section defines the last day after treatment for which these observations are included in the visit window.

For assignment of data to time points using the visit windows, study day will be defined as follows:

$$(\text{Date of assessment} - \text{Date of first dosing}) + 1.$$

In case of multiple observations within a single visit window, the following rules apply:

- If there are two or more observations within the same visit window, the observation closest to the target day will be used in the analysis
- If two observations are equidistant from the target day and the ties are on different sides of the target day, the observation with the earlier assessment date will be used in the analysis
- If two observations are equidistant from the target day and the ties located on the same sides of the target day (i.e. more than one observation for the same day but different time), the observation with the earlier (if the assessment day is equal or

larger than the target day) or later (if the assessment day is smaller than the target day) assessment time will be used in the analysis

- If two or more observations are collected on the same day, all non-missing but with no collection time associated with at least one of them, the average of the observations will be used in the analysis.
- If two or more observations are collected on the same day and time, and they are same closest to the target day, the average of the observations will be used in the analysis.

If a visit window does not contain any observation, then the data will be missing for that visit.

CCI  
visit date, then the average of the available non-missing measurements with that same visit date will be used in summary and analysis.

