3.9.2 Procedures for discontinuation of a patient from IP

A patient that decides to discontinue IP will always be asked about the reason(s) and the presence of any AEs. Diaries and all study drugs should be returned by the patient.

All patients who discontinue study drug will be asked to remain in the study for FU and complete all scheduled study visits through Week 27. At the time of discontinuation the Week 24 procedures will be performed. Patients will not receive double-blind study drug during this follow-up period (and use of SGLT2-inhibitors should be restricted), but will complete all scheduled study visits and procedures. Patients unable or unwilling to return for scheduled visits as part of follow-up will have the opportunity to receive follow-up via telephone calls placed by the site mainly to review safety and concomitant medications. The only exception to this procedure is when a patient withdraws consent for all study procedures or loses the ability to consent freely (i.e., is imprisoned or involuntarily incarcerated for the treatment of either a psychiatric or physical illness).

If a patient is withdrawn from study, see Section 3.10.

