4.3.5 Visit 8, End of Treatment/Discontinuation/Rescue

Randomized patients discontinuing study drug or requiring rescue should have Visit 8 (Week 24) procedures done at the time of rescue or study drug discontinuation. All patients who discontinue study drug will be asked to continue ordinary visit schedule, unless they entirely withdraw consent from the study.

- Perform complete physical examination
- Measure body weight CCI
- Obtain vital signs (seated and orthostatic BP and pulse)
- Obtain specimen (blood) for safety laboratory panel including S-Creatinine for eGFR calculation

CCI

- Perform urine pregnancy test for women of child bearing potential. Serum pregnancy test (β hCG) is performed, if urine pregnancy test result is positive
- Obtain specimen for urinalysis (dip stick and spot urine collection)
- Timed urine sample collection (24-hours) (see Section 5.1)
- Collect and assess compliance with study drug based on tablet count
- Provide dietary and life-style advice
- Dispense glucose meter supplies and diary (if required)
- Review diary and calculate mean total daily dose of insulin
- Review concomitant medications and AEs including hypoglycemic events
- Remind patient to be fasting and withhold anti-diabetic medications, insulin, anti-hypertensive drugs, lipid lowering drugs and anti-platelet drugs, the morning of their next visit and to refrain from tobacco/nicotine for 12 hours and alcohol for 24 hours, respectively prior to next visit

4.4 Follow-up period, Visit 9

Descriptions of the procedures for this period are included in the Study Plan [Table 1](#). The specific requirements for the follow up period are mentioned below:

After completion of Week 24 visit, patients will enter a 3-week safety follow-up period without study drug. The follow-up visit (Visit 9) provides the opportunity to further evaluate changes in physical signs, renal function (i.e., changes in eGFR), symptoms or laboratory parameters that may be related to dapagliflozin.

- Perform brief physical examination
- Measure body weight
- Obtain vital signs (seated and orthostatic BP and pulse)
- Obtain specimen (blood) for safety laboratory panel including S-Creatinine for eGFR calculation

CCI

- Perform urine pregnancy test for women of child bearing potential. Serum pregnancy test (β hCG) is performed, if urine pregnancy test result is positive
- Obtain specimen for urinalysis (dip stick and spot urine collection)

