### **Follow-up Period (V8 to V9, 3 weeks)**

After completion of the treatment period, patients will enter a 3-week safety follow-up period without study drug. At the follow-up visit (Visit 9 (FU)) any changes in physical signs, renal function (*i.e.*, changes in eGFR), symptoms or laboratory parameters that may be related to dapagliflozin will be evaluated. Patients who discontinue study drug will remain in the study for follow-up and complete all scheduled study visits through Week 27. At the time of discontinuation the Week 24 procedures will be performed. Patients will not receive double-blind study drug during this follow-up period, but will complete all scheduled study visits and procedures.

The total planned study duration from Visit 1 to the safety follow-up (Visit 9) will be 33 weeks.

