#### 4.1.3 Derivation of Efficacy Variable at Rescue/ Premature Discontinuation

In efficacy analyses, the glycemic parameters will only include measurements obtained prior to or on the date of rescue medication administration or discontinuation of double-blind medication (whichever is earlier). An exception would be in sensitivity analysis, where the analysis is performed on data regardless of rescue (see more details in Section 4.2.6.2).

For secondary efficacy variables of body weight (kg), seated SBP (mmHg) and remaining exploratory variables, measurements after rescue medication will not be excluded from the analyses.

Patients not completing the treatment period should have all Week 24 visit procedures done at the time of study discontinuation or rescue.

Patients who meet the pre-specified rescue criteria, at the specified visit described in Table 4, will be scheduled for a follow-up visit (within 3-5 days) to obtain a confirmatory central lab FPG value. If the confirmatory FPG value still meets the criteria, the patient will be rescued.

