**4.1.7.1 Multiple Imputation based on Retrieved Drop-outs (MI-RD)**

In MI-RD, all patients in the randomized set who have a baseline assessment (regardless of rescue or treatment discontinuation) will be included in the analysis. Based on status of whether the patients have early treatment discontinuation and whether the assessment is available at Week 24, the population will be categorized as 4 subpopulations described in [Table 6](#).

The main steps of the implementation of MI-RD are described below.

Step 1: Impute missing data for patients without HbA1c at Week 24 using a regression model imputation based on data from patients who discontinued treatment but had HbA1c assessment at Week 24 within that treatment group. The HbA1c baseline will be used as explanatory variable for imputation. If, for each (protocol-defined) visit where there is at least 1 patient with a last on-treatment assessment and is missing a Week 24 HbA1c value, there are (at that same visit) sufficient numbers of patients with a last on-treatment assessment that subsequently discontinued treatment but have a Week 24 HbA1c value, then the missing Week 24 HbA1c values will be imputed from the non-missing Week 24 HbA1c values by “last on-treatment visit” within each treatment group. Otherwise, if there are sufficient numbers of patients that discontinued treatment but have a Week 24 HbA1c value (regardless of last protocol-defined visit “on-treatment”) then missing Week 24 HbA1c values will be imputed from the patients that have discontinued treatment but have Week 24 HbA1c values within each treatment group. The imputation population and process are described in [Table 6](#). Imputation will be done within each treatment group.

Step 2: Analyze the multiple imputed HbA1c change from baseline at Week 24 using ANCOVA model. Combine estimates obtained from multiple imputed datasets based on Rubin’s combination rules ([Little R., Rubin D.B. 2002](#)).

The MI-RD approach requires a sufficient number of patients who discontinued treatment but had HbA1c assessment at Week 24 in each treatment. If there is not a sufficient number of patients to do the analysis, then this approach will not be implemented.

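### Table 17 can count an on-drug stop-visit HbA1c from day 128 onwards as an observed Week 24 value in the retrieved-dropout analysis (MI-RD)

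*SAP*

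**What the plan says.** **Windows.** SAP 4.3.1 assigns visits "based on the day of evaluation relative to the reference start date rather than the nominal visit recorded in the CRF". In Table 17 the HbA1c window for Week 24 is "128-Last day of DB period", with target day 169. If several values fall in one window, "the observation closest to the target day will be used in the analysis". SAP 4.1 applies these windows to the efficacy analyses and makes no exception for the imputation analyses.

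**Sampling when drug is stopped.** SAP 4.1.3: "Patients not completing the treatment period should have all Week 24 visit procedures done at the time of study discontinuation or rescue". SAP 1.2 (Follow-up Period): "At the time of discontinuation the Week 24 procedures will be performed". Protocol 4.3.5 says such patients "should have Visit 8 (Week 24) procedures done at the time of rescue or study drug discontinuation". HbA1c is among the Visit 8 samples in Protocol Table 1. Discontinuers are asked to keep attending, but Protocol 3.9.2 foresees that some will not: "Patients unable or unwilling to return for scheduled visits as part of follow-up will have the opportunity to receive follow-up via telephone calls". A telephone call yields no HbA1c.

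**MI-RD.** SAP Table 6 leaves Subpopulation 2 (stopped drug, Week 24 HbA1c present) as observed. It uses that group to estimate the imputation model for Subpopulation 3 (stopped drug, no Week 24 HbA1c) and Subpopulation 4 (not stopped, no Week 24 HbA1c). Step 1 in SAP 4.1.7.1 first imputes by last on-treatment visit, which requires "sufficient numbers of patients with a last on-treatment assessment that subsequently discontinued treatment but have a Week 24 HbA1c value". Failing that, it pools all discontinuers with a Week 24 value within the arm. If too few exist, MI-RD is not run; no number is given.

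**The concern.** The wording of Step 1 separates a last on-treatment assessment from a later Week 24 value in a patient who has since stopped. The donors are therefore meant to show what happens off drug. For a patient who stops on day 128 or later and does not return, the window rule merges the two: one sample, taken at or just after the last dose, is both. The nominal visit label would not separate them either, because the stop visit is also called Visit 8.

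MI-RD is one of only two planned analyses of the difference regardless of rescue or discontinuation (SAP Table 10). On-drug values in Subpopulation 2 pull it towards the primary result, which it is meant to test. They also count towards the unspecified number of retrieved patients that decides whether MI-RD is run.

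**Working it through.** **1. The plan's own figure.** SAP 4.3.1 sets window limits at the midpoint between visits. For days 85 and 169 this is (85 + 169)/2 = 127, so Week 24 starts on day 128, as Table 17 states. The opening is 169 − 128 = 41 days before target. The protocol's Visit 8 window is 169 ± 5, that is days 164–174.

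**2. Inputs.** From the documents: 151 patients per arm, SD 0.9, effect −0.3 (SAP 1.4). SE = 0.9 × √(2/151) = 0.104.

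Assumed, because the documents give no figures:
- Proportion discontinuing: p = 10% or 20%.
- Proportion of discontinuers returning for Visit 8: r = 25%, 50% or 75%.
- Last-dose day *d* uniform on 1–168, with the stop visit on day *d* + 1.
- Double-blind period fixed by calendar, so that returning patients' values near day 169 count as Week 24.
- Off-drug effect either lost at once (full loss) or lost linearly over 84 days, giving −0.3 × [1 − min(1, (169 − *d*)/84)] at day 169.

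**3. Share of stop visits in the window.** *d* + 1 ≥ 128 means *d* = 127 to 168: 42/168 = 0.25.

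**4. Share of Subpopulation 2 that are stop-visit samples.** s = 0.25(1 − r)/[r + 0.25(1 − r)] = 0.429, 0.200 and 0.077 for r = 25%, 50% and 75%. At p = 10%, genuine plus stop-visit donors per arm (151·p·r and 151·p·0.25·(1 − r)) are 3.8 + 2.8, 7.6 + 1.9 and 11.3 + 0.9.

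**5. Error in MI-RD (HbA1c percentage points, towards the primary result).**
- Pooled, full loss: 0.3·p·s.
- Pooled, linear loss: the mean off-drug effect over all *d* is −0.0741, so the error is (0.3 − 0.0741)·p·s = 0.2259·p·s.
- By visit, full loss: only the observed values matter, 0.3·p·0.25·(1 − r).
- By visit, linear loss: the mean loss for *d* = 127–168 is 25.6%, so the preceding figure is multiplied by 0.256.

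| Version | Loss | p | r = 25% | r = 50% | r = 75% |
|---|---|---|---|---|---|
| Pooled | full | 10% | 0.013 | 0.006 | 0.002 |
| Pooled | linear | 10% | 0.010 | 0.005 | 0.002 |
| Pooled | full | 20% | 0.026 | 0.012 | 0.005 |
| Pooled | linear | 20% | 0.019 | 0.009 | 0.003 |
| By visit | full | 10% | 0.006 | 0.004 | 0.002 |
| By visit | linear | 10% | 0.0014 | 0.0010 | 0.0005 |
| By visit | full | 20% | 0.011 | 0.0075 | 0.004 |
| By visit | linear | 20% | 0.003 | 0.002 | 0.001 |

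The largest entry relative to the SE is 0.0257/0.1036 = 0.25.

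**6. After excluding stop-visit samples before day 164.** Only *d* = 163–168 remain: 6/168 = 3.6%. The stop-visit share of Subpopulation 2 falls to 9.7%, 3.4% and 1.2%. At p = 20% and r = 25%, the pooled error falls from 0.026 to 0.006 (full loss) and from 0.019 to 0.004 (linear loss).

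**7. The same exclusion in washout imputation, linear loss.** Per non-returning discontinuer the true mean effect is −0.0741. Washout as written gives 0.25 × (−0.3) = −0.0750; with the exclusion it gives (6/168) × (−0.3) = −0.0107. At p = 20% and r = 25%, the absolute error rises from 0.2 × 0.75 × 0.0009 = 0.0001 to 0.2 × 0.75 × 0.0634 = 0.0095.

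**The case against.** The case for leaving the SAP alone is that midpoint windows are its stated convention, the affected analysis is a sensitivity analysis that may not be run, and the shift is small. The 0.25 SE figure needs 20% discontinuing, three quarters of them not returning, immediate total loss of effect and the pooled fallback, all together. This stands, and it sets the priority.

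It can also be argued that 4.1.7.1 speaks of protocol-defined visits, so that a day-130 sample was never meant as Week 24. This does not hold. The phrase describes the last on-treatment visit, and the general rule in SAP 4.1 applies Table 17 to the efficacy analyses.

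Four stronger readings are tempting, and the documents do not support them:

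- *The problem is the same wherever the double-blind period ends.* It is not. If the period ends on the last-dose date, a stop visit one day later falls in the follow-up row. If it ends a few days after last dose (SAP 4.2.7.2 uses 4 days for laboratory data, and the note under Table 17 points to the 8-day HbA1c rule in 4.3.2), the stop-visit sample counts as Week 24, while day-169 values of most discontinuers who return do not. True retrieved values are then lost, which is worse, and the table above no longer applies.
- *The samples act as donors in every version of MI-RD.* This is clear only for the pooled fallback. By last on-treatment visit, if that visit is also assigned by Table 17, these patients may sit in a Week 24 stratum with nobody to impute.
- *Washout imputation needs the same correction.* Washout also keeps the sample as observed, but step 7 shows that excluding it helps only if the effect disappears quickly.
- *Rescue-visit samples should go too.* Rescued patients remain on blinded drug. Excluding their samples could move a patient from Subpopulation 1 to Subpopulation 4, to be imputed from patients who stopped drug.

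**Conclusion.** The point holds for MI-RD. On a calendar-based double-blind period, SAP 4.3.1 and Table 6 together place non-returning late discontinuers in Subpopulation 2 with an on-drug value, when they belong in Subpopulation 3. The pooled fallback also uses that value to impute others, and it counts towards the feasibility condition. If the period instead follows each patient's last dose, genuine off-drug Week 24 values can be lost, so the term needs a definition in either case.

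Under the stated assumptions the error is 0.002–0.026 pooled and 0.0005–0.011 by visit, always towards the primary result. Discontinuation rate, return rate and loss of effect are all assumed, so these are illustrative ranges, not predictions. A reader might infer that the primary result is in doubt. It is not: the primary MMRM uses on-treatment values by design. This is a low-priority but well-defined correction.

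**What to change.** Add to SAP 4.1.7.1, with a cross-reference in 4.3.1:

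> For MI-RD, the Week 24 HbA1c is the value closest to day 169 from day 128 up to, but not including, the Week 27 follow-up visit, regardless of last dose date or rescue. For patients who discontinued double-blind drug, a sample taken at the discontinuation visit before day 164 (opening of the Visit 8 window, day 169 ± 5) is not a Week 24 value. Without a later value the patient belongs to Subpopulation 3.

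In 4.3.1, define the last day of the double-blind period and the first day of the follow-up period so that off-drug Visit 8 values of returning discontinuers fall in Week 24. Keep rescue-visit samples of patients who remain on blinded drug, set no earlier upper day limit that could turn a late on-treatment Visit 8 into a missing value, and leave the washout window as it is.

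Cost: a few sentences and one derived flag from dates already collected; no new data. The downside is that Week 24 is defined slightly differently in MI-RD than in the primary analysis, and MI-RD has fewer donors. At 10% discontinuing and 25% returning, for example, the count per arm falls from 3.8 + 2.8 to 3.8 + 0.4 (151 × 0.10 × 0.75 × 6/168), which may show that MI-RD is not feasible.

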2.3 Safety objectives

Safety Objective:	Outcome Measure :
To examine eGFR changes during the study and 3-week post-treatment for dapagliflozin 10 mg and placebo.	Change in eGFR from baseline to end of treatment and 3-week post-treatment
To assess the proportion of patients discontinued from study medication because of worsening renal insufficiency (defined as patients reaching confirmed eGFR levels $<30 \text{ mL/min/1.73 m}^2$) between dapagliflozin 10 mg and placebo.	Proportion of patients discontinued from study medication due to worsening renal insufficiency ($<30 \text{ mL/min/1.73 m}^2$) at the end of treatment
To evaluate the safety and tolerability of dapagliflozin 10 mg once daily in type 2 diabetes and CKD stage 3A.	AEs /SAEs Vital signs Physical examination Clinical chemistry parameters

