##### **4.1.6 Longitudinal Repeated Measures Analysis**

###### **4.1.6.1 Longitudinal Repeated Measures Analysis for Change from Baseline**

For changes from baseline to Week 24 in all efficacy parameters (e.g. HbA1c, FPG, and seated SBP etc.) and exploratory analysis on continuous endpoints (e.g. eGFR, CCI etc.), analyses will be based on a longitudinal repeated measures

(MMRM) analysis using “direct likelihood”. The SAS procedure PROC MIXED will be used. The preferred model for this analysis will include the fixed categorical effects of treatment, week, randomization stratification factor (i.e. anti-diabetic treatment strata), and treatment-by-week interaction, as well as the continuous fixed covariates of baseline measurement and baseline measurement-by-week interaction.

An unstructured covariance structure will be used to model the within-patient error. The Kenward-Roger approximation (Kenward and Roger, 1997) will be used to estimate denominator degrees of freedom.

In case of non-convergence of the preferred model or memory space issues, the following back-up models are defined:

- The first backup model is the same as the preferred model but the Kenward-Roger method will be replaced by Satterthwaite approximation.
- The second backup model is the same as the preferred model but without the term for baseline measurement-by-week interaction.

The second back-up model will only be provided if the first back-up model does not converge or has memory issues.

The mixed model will provide least-squares mean estimates, standard errors and 2-sided 95% confidence intervals within each treatment group. The differences in least-squares means, 2-sided 95% confidence intervals and p-value of the differences in week 24 visit estimates between dapagliflozin and placebo will be presented as well.

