#### **4.2.7.2 Clinical Laboratory Tests Evaluation**

Unless otherwise specified, laboratory data obtained after the start of study medication dosing up to and including 4 days (30 days for liver function laboratory test) after the last double-blind dosing date will be considered as obtained during the double-blind treatment period. Laboratory data obtained from the day after the last study medication +4 days (30 days for liver function laboratory test) up to the last visit date of the follow-up period will be considered as obtained during the follow-up period.

For liver safety, a summary of proportion of patients with elevated liver test (see Appendix C for definition) will be provided for the double-blind treatment period. In addition, a summary of proportion of patients with elevated liver test and/or reported AE of hepatic disorder will also be provided for the double-blind treatment period.

All scheduled laboratory evaluations are performed by central laboratories. All laboratory evaluations performed by central laboratories will be included in summary tables.

Laboratory parameters will be presented in international system units, except for those listed in Table 16, which will be presented in conventional units (C) and international system units (SI).

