#### **4.2.7.2.2 Changes from Baseline Values for Selected Laboratory Parameters over Time**

All analyses of laboratory data will use observed data regardless of rescue. Visit windows are provided in Section 4.3.1 in order to link each laboratory test to a scheduled visit. Change from baseline during the double-blind treatment period and the follow-up period for selected laboratory parameters will be summarized by treatment group, presenting n's, means, medians, minimum, maximum, SEs:

Hematology parameters:

- hemoglobin
- hematocrit
- red blood cell (RBC) count
- white blood cell (WBC) count
- platelet count

Serum Chemistry parameters:

- aspartate aminotransferase (AST)
- alanine aminotransferase (ALT)
- alkaline phosphatase
- total bilirubin
- blood urea nitrogen (BUN)
- electrolytes - sodium, potassium, bicarbonate, chloride, magnesium, calcium
- total protein and albumin
- creatinine, serum (Scr)
- Estimated eGFR (mL/min/1.73m^2) using MDRD equation

CCI

Urine parameters:

- Creatinine

CCI

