#### **4.2.7.2.3 Additional Laboratory Data Summaries**

##### Shift Tables for Electrolytes (Sodium, Potassium, Calcium, Phosphate, and Magnesium) Categories

Shift tables of Safety Data Set patients with electrolytes values in categories of low, normal, and high (based on normal range of central laboratory) will be summarized by treatment group using the highest (for sodium, calcium, phosphate, and magnesium) and lowest (for sodium, potassium, and calcium) values (regardless of rescue) obtained during the double-blind treatment period.

CCI

will be summarized by treatment group using the Week 24 values (the last observation regardless of rescue prior to Week 24 will be used if no Week 24 measurement is available).

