#### 4.3.2 Post-Dosing Efficacy Observations

While double blind treatment period efficacy observations will be listed regardless of whether the patient was taking blinded study drug. Observations will be included in summarizes of the FAS only if the following rules are satisfied:

- HbA1c, body weight, BMI and CCI will be summarized only if measured on or before the 8th day after the last double-blind drug dosing date.
- FPG, CCI SBP, eGFR and Insulin initiation will be summarized only if measured on or before the 1st day after the last randomized, double-blind drug dose date.
- Lipids and other exploratory parameters (if available) will be summarized only if measured on or before the 4th day after the last randomized, double-blind drug dose date.
- The efficacy measurements of HbA1c and FPG will be summarized/analysed only if measured on or prior to the first dose of rescue medication.

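### The visible by-visit eGFR safety summary has no row defined as end of treatment or as 3 weeks after the last dose, so for early stoppers it does not deliver the stated eGFR outcome

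*SAP*

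**What the plan says.** Protocol 2.3 gives the outcome for the first safety objective as "Change in eGFR from baseline to end of treatment and 3-week post-treatment".

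The visible SAP analysis of it is in 4.2.7.2.2: "Change from baseline during the double-blind treatment period and the follow-up period for selected laboratory parameters will be summarized by treatment group". MDRD eGFR is in that section's serum chemistry list, so the safety-laboratory column of Table 17 is its natural home. SAP 4.3.1 says that visit designation "will be based on the day of evaluation relative to the reference start date rather than the nominal visit recorded in the CRF".

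In Table 17, Week 4 covers Days 2-57, Week 12 covers Days 58-127, and Week 24 runs from Day 128 to the last day of the double-blind period. One row, Follow-up Week 27 (target Day 190), covers the whole follow-up period. Within a window, "If there are two or more observations within the same visit window, the observation closest to the target day will be used in the analysis". An empty window is treated as missing.

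SAP 4.2.7.2 counts laboratory values as double-blind up to 4 days after the last dose. The follow-up period takes what comes later, through its final visit: "Laboratory data obtained from the day after the last study medication +4 days (30 days for liver function laboratory test) up to the last visit".

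Protocol 3.9.2 requires the Week 24 procedures when study drug is stopped, then all scheduled visits through Week 27. Table 1 footnote e, Protocol 4.3.5 and the follow-up paragraph of SAP 1.2 agree. Protocol 1.4, however, describes a 3-week follow-up after either completion or discontinuation.

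**The concern.** Both halves of the outcome are defined by when treatment ended, while the windows are anchored on the first dose. For a patient who completes on schedule the two clocks agree. For a patient who stops early they do not: the sample taken at stopping loses its end-of-treatment role, and the follow-up row reports a study day instead of a time off drug.

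Renal safety is in the study title, and a confirmed eGFR below 30 mL/min/1.73 m² is itself a reason to stop study drug (Protocol 3.9.1), so early stoppers matter for this outcome. As planned, the rows cannot be read for them as the change at the end of treatment and the change 3 weeks after it.

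**Working it through.** **Inputs.** Serum creatinine is drawn after randomization on Days 29, 85, 169 and 190 (Protocol Table 1) and at stopping (Protocol 3.9.2). Windows and selection rule: SAP Table 17. Laboratory on-treatment limit: last dose + 4 days (SAP 4.2.7.2). Let L be the study day of the last dose. Scheduled samples are taken as on target, and the stopping sample as taken on day L.

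**1. The plan's own figures.** The window bounds are midpoints: (29 + 85)/2 = 57 and (85 + 169)/2 = 127, so Week 24 opens on Day 128, as Table 17 states. For an on-schedule completer 190 − 169 = 21 days, so the follow-up row is right for that patient.

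**2. Week 24 row.** It is empty whenever L + 4 < 128, that is for L ≤ 123 (123 + 4 = 127). For L = 124-127 it is filled only if the stopping sample is taken on Day 128 or later, within L + 4.

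**3. Where the stopping sample goes when L ≤ 123.**
- L about 1-24: it stays in the Week 4 row.
- L = 25-28: it is displaced if the Day 29 visit is attended, because Day 29 ≤ L + 4 is still on treatment.
- L = 30-57: it is displaced by an on-target Day 29 sample.
- L = 58-80: it stays in the Week 12 row.
- L = 81-84: it is displaced if the Day 85 visit is attended.
- L = 86-123: it is displaced by an on-target Day 85 sample.

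If a scheduled Day 29 or Day 85 value triggered the stop, that value remains in its row.

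**4. Days off drug in the Follow-up Week 27 row.** The follow-up period starts at L + 5, and the value nearest Day 190 is used.

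| Situation | Formula | Days off drug |
|---|---|---|
| L = 1-123, Visit 9 on Day 190 | 190 − L | 67-189 |
| Same, Visit 9 within ±5 days | 185 − 123 to 195 − 1 | 62-194 |
| L = 1-123, last sample Day 169 | 169 − L | 46-168 |
| L = 1-80, last sample Day 85 | 85 − L | 5-84 |
| L = 124-167, Visit 9 on Day 190 | 190 − L | 23-66 |
| Completer, both visits on target | 190 − 169 | 21 |
| Completer, ±5 days at both visits | 185 − 174 to 195 − 164 | 11-31 (32 if the last dose is the day before Visit 8) |

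**5. Usable 3-week samples are passed over.** For L = 64 the Day 85 sample is exactly 21 days off drug; for L = 148 the Day 169 sample is. If the Day 190 sample exists, the rule selects it instead, at 126 and 42 days. For L ≤ 123, an extra sample at L + 21 falls on Day 144 at the latest, so it also loses to any Day 169 or Day 190 sample.

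**6. Scheduled coverage of a last-dose window.** In [L + 11, L + 32], for L = 1-123, the Day 29 sample serves L = 1-18 and the Day 85 sample serves L = 53-74. Nothing scheduled serves L = 19-52 (34 days) or L = 75-123 (49 days): 34 + 49 = 83 of 123 last-dose days.

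**7. The exploratory eGFR model.** The repeated-measures model in SAP 4.1.6.1 targets Week 24. SAP 4.3.2 is tighter for summaries of the Full Analysis Set: "eGFR and Insulin initiation will be summarized only if measured on or before the" first day after the last dose. There Week 24 is empty for L + 1 < 128, that is L ≤ 126, and a stopping sample 2-4 days after the last dose is left out.

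**The case against.** **A last-value eGFR analysis may exist under redaction.** SAP 4.1.5 makes carry-forward of the last post-baseline value the default for ANCOVA. SAP 4 allows ANCOVA for exploratory continuous endpoints, and eGFR is named as one in 4.1.6.1. The rows of Table 12 are blacked out, but the table has a column for LOCF or observed values. SAP 4.2.7.2.3 has a rule that "the last observation regardless of rescue prior to Week 24 will be used if no Week 24 measurement is available", with its subject redacted. Table 17 has a column with a redacted header whose Week 24 window opens on Day 2. This stands as a limit. A reader might infer that the plan has no end-of-treatment eGFR analysis at all; the documents support that only for the visible summary.

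**An empty Week 24 row is normal in an observed-data, by-visit, on-treatment table.** True, and SAP 1.1.3 and Protocol 8.4.3 do not use the term end of treatment for eGFR change. But the outcome column of Protocol 2.3 does, and Visit 8 is the visit for end of treatment, discontinuation and rescue alike. SAP section 6 declares no change from the protocol.

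**The stopping value is not lost.** Correct for last doses on about Days 1-24 and 58-80, where it is summarized under Week 4 or Week 12. Elsewhere displacement needs a scheduled sample nearer the target. A reader might infer that the plan discards the stopping eGFR; it remains in the data, but no visible row identifies it as end of treatment.

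**Severe declines are captured elsewhere.** Partly so: discontinuations for eGFR below 30 (Protocol 8.4.3), renal events of special interest (SAP 4.2.7.1.6), and marked creatinine abnormalities with all values of the patient listed (SAP 4.2.7.2.1, Appendix C). None of these is the eGFR change at the two stated times.

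**The follow-up gap depends on the schedule read.** If Protocol 1.4 alone governed, the gap would be about 21 days. The other four passages describe the ordinary schedule through Week 27.

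**Conclusion.** The point holds for patients who stop early. The visible summary leaves Week 24 empty for every last dose by Day 123. Under the schedule through Week 27, its single follow-up row holds values 67 to 189 days off drug when Visit 9 is on Day 190, and as few as 5 days when Day 85 is the last sample, beside completers at about 21. These figures assume on-target scheduled visits except where the ±5-day window is shown, and that the safety-laboratory column applies to eGFR.

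They are ranges of calendar days, not patients. The documents give no distribution of stopping times, so the number affected and any distortion in mL/min/1.73 m² cannot be derived. A reader might infer that the windows favour dapagliflozin by hiding renal decline. The documents do not support that: the rule is the same in both arms, its direction cannot be worked out, and the summaries are descriptive with no between-arm testing (Protocol 8.5.7). This is a stated rule that misses the stated outcome for a subset, and it is worth correcting because correction is cheap.

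**What to change.** In SAP 4.2.7.2.2 and 4.3.1, for eGFR and creatinine:

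1. Unless a redacted table already does so, add an end-of-treatment row: the last post-baseline value on or before last dose + 4 days, for all treated patients with such a value. Show it beside the by-visit rows with time on drug by arm.
2. Keep the Follow-up Week 27 row, do not present it as 3-week post-treatment for early stoppers, and report time off drug by arm.
3. Report the 3-week post-treatment change only from the sample nearest last dose + 21 days within a bounded window, for example +11 to +32 days, which is the spread that the visit windows already allow completers. Give n by arm and state that early stoppers will often have no such sample.
4. Reconcile Protocol 1.4 with Protocol 3.9.2, Table 1 footnote e, Protocol 4.3.5 and SAP 1.2 on follow-up after discontinuation.

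The cost is SAP wording and two table rows from samples already planned. The end-of-treatment row pools different exposure times, which is why time on drug must sit beside it. The 3-week row will be thin for early stoppers and must not be read as covering the same patients as the end-of-treatment row.
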